## 9.2 Safety Parameters

### 9.2.1 Safety Parameters

Safety parameters will include adverse events, AEs, unanticipated AEs, ADEs, and UADEs.

### 9.2.2 Safety Analysis

Safety data will be summarized descriptively, using descriptive statistics and/or counts and percentages. Statistical analyses will not be performed on safety data.

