This material is the property of Stryker Spine. Do not disclose or use except as authorized in writing by Stryker.  
Page 11

Ancillary Devices	
The AccuLIF system is indicated for use with autogenous bone and/or allograft (cancellous or corticocancellous allograft chips) and supplemental fixation. Stryker supplementation fixation (Xia or ES2 pedicle screws must be used as part of the study protocol).

Statistical Methodology	
All continuous data will be summarized using continuous descriptive statistics: number of subjects with responses (n), mean, standard deviation, median, minimum, and maximum. Changes from baseline, where appropriate, will be calculated as the follow-up measure minus the baseline measure, where baseline is defined as the last measure prior to the AccuLIF spinal system surgical procedure.
 
All categorical data will be summarized using counts and percentages. Denominators for percentages will be the number of subjects in the respective patient population with nonmissing data.
 
For the primary endpoint of an increase of 3 degrees or more of segmental lordosis, a one-sided analysis (<math>\alpha=0.05</math>) will be used to assess significance. A one-sample t-test will be employed. Although the primary analysis will be at 24 months, similar analyses will be performed at each visit. Both the change from baseline and the results at each visit will be summarized.
 
For all other radiographic parameters, the change from baseline will be analyzed at each visit using two-sided, one-sample t-tests (<math>\alpha=0.05</math>) comparing the change from baseline to 0.
 
Secondary and exploratory endpoints will be analyzed where appropriate. Where changes from baseline can be calculated for numerical data, statistical analyses will be performed. Analyses will follow the two-sided approach taken for the primary analyses. Data that is ordinal in nature, such as the changes in clinical outcomes, may be analyzed using Wilcoxon signed rank tests, comparing baseline measures to follow-up measures. All analyses will be two-sided and evaluated at an alpha level of 0.05.

CONFIDENTIAL

This material is the property of Stryker Spine. Do not disclose or use except as authorized in writing by Stryker.  
Page 12

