#### 9.1.4 Secondary Objective Parameters

The secondary parameters of the study, evaluated at each study visit, are as follows:

- Surgical parameters of the AccuLIF cohort, including operative time, estimated blood loss and length of stay.
- The occurrence of neurologic complications, defined as abnormal changes from the pre-operative to post-operative neurologic evaluations.
- Changes in clinical outcomes, comparing pre- and post-operative patient measured outcomes defined as VAS, ODI and quality of life (QOL) as measured by SF-12.
- The occurrence and frequency of additional complications of the AccuLIF cohort, including infection and nonunion.
- Standard radiographic outcomes defined as; fusion status, cage placement, migration / subsidence and parameters of supplemental fixation hardware including screw placement and subsidence.

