#### 9.1.5 Secondary Objective Analysis

Where changes from baseline can be calculated for numerical data, statistical analyses will be performed. Analyses will follow the two-sided approach taken for the primary analyses. Data that is ordinal in nature, such as the changes in clinical outcomes, may be analyzed using Wilcoxon signed rank tests, comparing baseline measures to follow-up measures. All analyses will be two-sided and evaluated at an alpha level of 0.05.

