#### **9.6 Safety Patient Population**

All patients who undergo the surgical procedure (lumbar interbody fusion via the transforaminal approach with the AccuLIF Expandable Interbody Fusion Cage with internal supplemental fixation in the form of pedicle screws) will be included in the safety patient population.

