## 10.3 Early Withdrawal of Subjects

### *When and How to Withdraw Subjects*

In the event that the subject is discontinued by the investigative center prior to the final study evaluation, the subject will be notified by the center that he/she is no longer in the study and a Study Termination CRF will be completed.

The following is a list of reasons for which subjects may be withdrawn and the date of termination that should be used on the Study Termination CRF in each situation. This list is not all inclusive:

Termination Reason	Date of Termination
Death	Date of death
Investigative center termination	Date of study close-out visit
Lost to follow-up	Date Stryker termination approval given
Voluntary withdrawal	Date subject notified center of withdrawal
Removal of study device	Date of removal procedure
Study device not implanted	Date of surgery
Surgery not performed	Date Stryker termination approval given

At the time of study surgery it is required that the following components are implanted: AccuLIF interbody implant, supplemental fixation via pedicle screws, bone graft (autogenous and / or corticocancellous allograft chips).

CONFIDENTIAL

This material is the property of Stryker Spine. Do not disclose or use except as authorized in writing by Stryker.  
Page 29

Revision or removal of the AccuLIF Cage System constitutes a failure and study termination for the subject.

If revision of supplemental fixation is required during the study, the event is considered a reoperation and does not constitute a failure or study termination.

If the subject fails to return for his/her follow-up appointments, every effort should be made to contact the subject to assess his/her health status. If, after attempting to contact the subject through three documented phone calls and a certified letter, the subject still does not respond, he/she will be considered lost to follow-up. A Study Termination CRF will be completed **only after notifying Stryker of the subject's status and being given approval to terminate.**

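### Event and complication rates are planned without any measure of precision: 9.2.2 rules out statistical analysis of safety data, and 9.1.5 gives no method for binary secondary outcomes

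*Combined protocol and SAP*

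**What the plan says.** Section 9.2.1 defines the scope of safety data: "Safety parameters will include adverse events, AEs, unanticipated AEs, ADEs, and UADEs". Serious AEs are not named there, although 8.2 defines them and 8.1.1 makes them reportable. Section 9.2.2 then gives the method, "Safety data will be summarized descriptively, using descriptive statistics and/or counts and percentages", and closes with "Statistical analyses will not be performed on safety data".

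Complications sit elsewhere. Section 9.1.4 lists abnormal neurologic change as a secondary parameter and, separately, "The occurrence and frequency of additional complications of the AccuLIF cohort, including infection and nonunion". These fall under 9.1.5: "Where changes from baseline can be calculated for numerical data, statistical analyses will be performed". That section adds Wilcoxon signed rank tests for ordinal data and gives no method for a yes/no outcome.

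Two rules bear on the denominator. The synopsis says "Denominators for percentages will be the number of subjects in the respective patient population with nonmissing data". Section 9.6 defines the safety population as "All patients who undergo the surgical procedure". The plan does not say what nonmissing means for an adverse event.

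The missing-data rule in 9.3 does not address events. Surgical interventions are recorded apart from AEs (8.5), with no analysis stated. Under 10.3, revision or removal of the cage ends a subject's participation.

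**The concern.** A bare percentage from about 100 subjects does not show what risk the data leave open. Section 1.1 gives limited knowledge of the benefits and harms of expandable cages as part of the reason for the study, and 9.1.6 and 12.5 plan comparisons with published results. Without an interval and a defined follow-up, an AccuLIF complication rate is hard to set beside a published one.

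A second issue is incomplete follow-up. If a cumulative percentage uses all operated subjects, anyone who leaves early counts as event-free for the rest of the 24 months. If it uses only subjects with data, the figure depends on how those who left differ from those who stayed. The plan does not say which applies to which outcome.

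**Working it through.** **1. The plan's own sample size.** Inputs from 9.4.2: true change 5 degrees against a margin of 3, SD 6, one-sided alpha 0.05, power 90%.

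- Normal approximation: (6 × (1.645 + 1.282) / 2)² = 77.1, so 78.
- Noncentral t: 79 (power 0.902), as stated.
- Dropout of 20%: 79 / 0.80 = 98.75, so 99, against 100 planned.

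The figure reproduces. It rests on lordosis only; the documents state no precision for any event rate.

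**2. What few events leave open.** With 0 events in n subjects, the exact two-sided 95% upper limit is 1 − 0.025^(1/n). Other rows are Clopper-Pearson limits. The event counts are illustrative.

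| Events / n | Exact 95% interval |
|---|---|
| 0/100 | 0 to 3.6% |
| 2/100 | 0.2 to 7.0% |
| 5/100 | 1.6 to 11.3% |
| 0/80 | 0 to 4.5% |
| 2/80 | 0.3 to 8.7% |
| 8/80 (for example, nonunion at 12 months) | 4.4 to 18.8% |

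The chance of seeing no event at all is (1 − p)^n. For a true risk of 1% it is 37% with 100 subjects and 45% with 80; for 2% it is 13% and 20%.

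**3. Dropout when all operated subjects form the denominator.** Assumptions not in the documents: constant event and dropout hazards, non-informative dropout, and the 20% of 9.4.2 (given for the 12-month endpoint) applied at 24 months. Let a = −ln(1 − true risk) and d = −ln(0.80) = 0.2231. The crude proportion is a/(a + d) × (1 − exp(−(a + d))).

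- True risk 10%: a = 0.1054, so 0.1054/0.3285 × (1 − 0.72) = 0.0898, or 9.0%.
- True risk 5%: 4.5%. True risk 20%: 18.0%.

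The relative understatement is about 10%. The range around it is wide:

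- If all dropout precedes the events, 10% shows as 0.8 × 10% = 8%.
- If all dropout follows them, it shows as 10%.
- If events fall within six weeks, the share of subjects lost by then is 1 − 0.80^(1.5/24) = 1.4%, so 10% shows as no less than about 9.9%.

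**4. Dropout when only nonmissing subjects form the denominator.** Take 12-month nonunion of 10% in the 80% of subjects with a result. If the rate in the missing 20% is m, the full-cohort rate is 0.8 × 10% + 0.2 × m. That is 8% for m = 0, 10% for m = 10%, and 14% for m = 30%. The observed 10% may be too high or too low.

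**The case against.** Descriptive safety reporting without tests is a common choice in a single-arm, post-market study of a cleared device. The plan sets no safety hypothesis or threshold, and anyone can compute an exact interval from a reported count and denominator. This stands as an argument against adding tests. It does not answer the request for intervals, which are compatible with descriptive reporting and which the last sentence of 9.2.2 could be read to forbid. The reader's own calculation also needs a denominator that the plan does not fix.

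Several stronger readings are tempting, and the documents do not support them:

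- *Analysis is ruled out for all complications.* The exclusion covers the 9.2.1 parameters. Neurologic complications, infection and nonunion come under 9.1.5, where analysis is allowed; the gap there is an unspecified method.
- *Dropout biases the complication rates low.* This follows only for events counted over all operated subjects. It is close to nil for perioperative events, and on the synopsis's nonmissing denominator the direction is open.
- *Time at risk is overstated*, because a subject lost to follow-up gets the termination date "Date Stryker termination approval given" (10.3). That date enters no planned estimate. It would matter only if a time-to-event analysis used it for censoring.
- *Zero events would count as proof of safety.* The plan does not say so.

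The dropout effect is also small: one percentage point on a 10% risk, well inside the interval widths above. Finally, a Kaplan-Meier remedy has its own weakness. Because cage revision or removal ends participation, censoring at that point is probably informative, so the remedy has to deal with it.

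**Conclusion.** The point holds as a gap in precision and in the handling of follow-up. Section 9.2.2 confines safety data to counts and percentages, 9.1.5 gives no method for binary outcomes, and so no event rate carries an interval. This matters most for rare events: none seen in 100 subjects is compatible with a risk of 3.6%, and none in 80 with 4.5%. These limits need no assumption beyond independent subjects.

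The dropout effect is secondary and conditional. A 10% risk shown as 9.0% rests on constant hazards, non-informative dropout, 20% loss by 24 months and an all-operated denominator; the same 20% loss gives anything from 8% to 10% as the timing varies. For visit-based outcomes no direction can be claimed.

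The change is a worthwhile, low-cost improvement. It leaves the primary analysis untouched.

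**What to change.** - **9.2.2:** replace the last sentence with wording such as: *Safety data will not be subjected to hypothesis tests; each event proportion will be reported with an exact 95% confidence interval.*
- **9.1.5:** apply the same intervals to the binary outcomes of 9.1.4. For 12-month CT nonunion, use subjects with an evaluable CT as the denominator and report how many lack one. Report visit-assessed neurologic change by visit.
- **Denominators:** name the safety population of 9.6 for AEs, SAEs, ADEs and surgical interventions, and say that the synopsis's nonmissing rule applies to visit-based outcomes.
- **Key events that accrue over time** (infection, SAEs, ADEs, cage revision or removal): also report cumulative incidence at 12 and 24 months with 95% intervals, censored at last contact. Treat cage revision or removal as an event or a competing event, not as ordinary censoring. Record the last-contact date beside the termination date.

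The cost is some plan wording, one extra date field and a few more tables. Reported risks for events that accrue over time may come out slightly less favourable.

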## 9.3 Missing Data

The primary analyses will be based on observed data. In addition, sensitivity analyses will be performed including missing data using a Markov Chain Monte Carlo multiple imputation method and using the last observation carried forward.

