#### 9.1.3 Primary Objective Analysis

CONFIDENTIAL

This material is the property of Stryker Spine. Do not disclose or use except as authorized in writing by Stryker.  
Page 25

For the primary endpoint of an increase of 3 degrees or more of segmental lordosis, a one-sided analysis (alpha=0.05) will be used to assess significance. A one-sample t-test will be employed. Although the primary analysis will be at 12 months, similar analyses will be performed at each visit. Both the change from baseline and the results at each visit will be summarized.

For all other radiographic parameters, the change from baseline will be analyzed at each visit using two-sided, one-sample t-tests (alpha=0.05) comparing the change from baseline to 0.

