### 9.4.2 Sample Size Calculation

CONFIDENTIAL

This material is the property of Stryker Spine. Do not disclose or use except as authorized in writing by Stryker.  
Page 27

Sample size calculations are based on the primary analysis of the change from baseline in segmental lordosis at 12 months, utilizing a one-sided, one-sample t-test. Based on previous experience it is assumed that the true change in segmental lordosis after 12 months will be 5 degrees. It is also determined that a change of at least 3 degrees is considered clinically meaningful. With a standard deviation of up to 6 degrees and assuming 90% power, 79 subjects are required to show a difference of at least 3 degrees. Assuming a dropout rate of up 20%, 100 subjects will be enrolled.

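### The primary success test drops every subject without a 12-month film; earlier post-operative films count only in sensitivity analyses, so the comparison with 3 degrees depends on who returns

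*Combined protocol and SAP*

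**What the plan says.** Section 9.1.3 sets the test: "a one-sided analysis (alpha=0.05) will be used to assess significance", followed by "A one-sample t-test will be employed. Although the primary analysis will be at 12 months, similar analyses will be performed at each visit". Section 9.1.2 places the threshold at a 3-degree increase in segmental lordosis. Section 9.3 adds that "The primary analyses will be based on observed data". Its next sentence plans two sensitivity analyses, Markov chain Monte Carlo multiple imputation and last observation carried forward. It does not specify the imputation model, and no rule covers disagreement with the primary test.

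Section 9.4.2 sizes the study on the same test: "it is assumed that the true change in segmental lordosis after 12 months will be 5 degrees", with SD up to 6 degrees, 90% power and 79 evaluable subjects. It then states: "Assuming a dropout rate of up 20%, 100 subjects will be enrolled".

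The Evaluation Schedule and sections 7.3 to 7.5 place AP/lateral films at 6 weeks, 3 months and 6 months. Section 9.5 admits to the efficacy population anyone enrolled who has any radiographic follow-up. Section 10.3 treats cage revision or removal as a failure and ends that subject's participation. Sections 5.2 and 6.2 confirm that there is one arm and no control.

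The Study Synopsis gives a different primary time point: "Although the primary analysis will be at 24 months, similar analyses will be performed at each visit".

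**The concern.** A one-sample t-test at a single visit has no term for other visits. A subject filmed at 6 weeks, 3 and 6 months but not at 12 months is in the efficacy population and yet adds nothing to the success decision. The completers' mean estimates the mean for all treated subjects only if absence at 12 months is unrelated to the correction, including what the earlier films already show. In a single-arm comparison with a fixed 3 degrees there is no second arm in which selection could cancel, so any shift in the completers' mean passes straight into the test.

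Two things are at stake: some precision from films the study takes anyway and, more importantly, protection against a success claim that depends on who came back. Section 10.3 also supplies an exit tied to the device. A subject whose cage is revised or removed before 12 months is declared a failure and then falls out of the primary test.

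**Working it through.** **Inputs from the documents.** Threshold 3 degrees, assumed true gain 5 (difference 2), SD 6, one-sided alpha 0.05, power 90%, 79 evaluable, 100 enrolled, dropout up to 20% (sections 9.1.3 and 9.4.2).

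**Assumed, because the documents give neither.** The correlation r between an early change and the 12-month change, taken as 0.6 to 0.9; and the dropout mechanism.

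**1. The plan's own figure.** With a noncentral t and noncentrality (2/6)√n, n = 79 gives power 90.2%, so 79 is reproduced. 79/0.80 = 98.75, or 99, stated as 100. With 20% missing, n = 80: SE = 6/√80 = 0.671 and power 90.5%. The planned power is met.

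**2. Precision from the earlier films.** Let M be the number of subjects with at least an early film, 80 of whom also have the 12-month film. The likelihood estimate of the 12-month mean has variance 36 × [(1 − r²)/80 + r²/M], and effective n = 36/variance.

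| r | All 20 dropouts have an early film (M = 100): SE, power | Half have one (M = 90): SE, power |
|---|---|---|
| 0.6 | 0.646, 92.3% | 0.657, 91.5% |
| 0.8 | 0.626, 93.6% | 0.647, 92.3% |
| 0.9 | 0.614, 94.4% | 0.640, 92.7% |

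For example, r = 0.8 and M = 100 gives 36 × (0.36/80 + 0.64/100) = 0.392, whose square root is 0.626. With no dropout at all, power would be 95.2%.

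**3. Selection, general form.** Bias of the completers' mean = 0.20 × (stayers' mean − leavers' mean at 12 months). Gaps of 1, 2 and 3 degrees give biases of 0.2, 0.4 and 0.6. At a true mean of exactly 3 degrees, the noncentral t with noncentrality bias/0.671 gives one-sided error of about 9%, 15% and 22% instead of 5%.

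**4. Selection acting through the 6-month film.** Suppose the dropouts' 6-month gain is 2.9 degrees below the stayers'. With equal SDs, the 12-month gap is r × 2.9, so bias is 0.20 × r × 2.9:
- r = 0.6: 0.35 degrees
- r = 0.8: 0.46 degrees
- r = 0.9: 0.52 degrees

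Simulation (100 subjects, 20% missing, logistic dropout on the 6-month value) agrees. It gives one-sided error of about 13% at r = 0.6, 17% at 0.8 and 19-20% at 0.9. The likelihood estimate using the 6-month film has bias near 0 and error near 5%.

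**5. The same pattern reversed.** If well-corrected subjects are the ones who leave, the t-test is conservative, with error about 1%.

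**6. Where the remedy falls short (r = 0.8, same dropout slope).** If half the dropouts lack the early film, the likelihood error is about 9-10%. If dropout depends on the unseen 12-month value, it is about 9%, against about 21% for the t-test.

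**The case against.** The other side has four good arguments.

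*The earlier films are not ignored.* Section 9.3 plans multiple imputation and last observation carried forward, both of which can use them, and a divergence from the primary result would be visible. This stands. The point concerns which analysis carries the success decision. What remains open is that the imputation model is unspecified and nothing is said about disagreement.

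*Power is not short.* A reader might infer that the study is underpowered. It is not: enrolling 100 to keep 79 or 80 already pays for the loss. The gain in step 2 is small, and smaller still if dropouts lack early films. Section 10.3 lists subjects whose surgery is not performed or whose device is not implanted, and they have no study post-operative film at all.

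*The dropout mechanism is not documented.* A reader might take 17% as the trial's false-positive rate, or push to a 5.2-degree gap, where the error is about 34-36% at r = 0.8. The documents do not support either. Nothing links attendance to early lordosis. Section 15.3 names loss of insurance as a cause of attrition and offers reimbursement, and section 10.3 requires three documented calls and a certified letter. The larger gap would need about 52% dropout in the worst-corrected tenth of subjects against 3% in the best. The direction could also be the reverse.

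*The remedy is not a cure.* Holding 5% error follows from letting dropout depend only on a film that is always observed; step 6 shows the rest. A model would also predict 12-month lordosis for a subject terminated after cage revision or removal as if the cage had stayed in place. This stands, and the fix must deal with it.

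**Conclusion.** The point holds as a cheap improvement to the primary analysis, not as a demonstrated error. As written, the success decision rests on subjects with an observed 12-month film, and it is valid only if missing that film is unrelated to the correction already seen. The stated 90% power is met. Precision is the lesser reason to act, worth roughly 1 to 4 percentage points of power for an assumed correlation of 0.6 to 0.9. Selection is the main reason, but its size is conditional: the 0.35-0.5 degree bias and 13-20% error require a 2.9-degree shortfall in dropouts' 6-month gain, a figure assumed here and not taken from the protocol.

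An analysis using the earlier films replaces the assumption that dropout is unrelated to outcome with a weaker one, missing at random given those films. In the scenarios where dropouts had the poorer correction, it did better than the t-test even when that weaker assumption failed, though it did not always hold 5%.

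**What to change.** In sections 9.1.3 and 9.3:

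- Make the primary analysis a repeated-measures model (MMRM) of change in segmental lordosis on all post-operative films, with visit as a factor and unstructured covariance. Test the 12-month mean against 3 degrees at one-sided 0.05. Alternatively, make the multiple imputation already planned primary, with the earlier visits named in its model.
- Keep the observed-case t-test as a sensitivity analysis.
- State how subjects terminated for cage revision or removal enter the analysis, so that a declared failure is not modelled as if the cage were still in place.
- State how two-level subjects enter, since lordosis is measured at each treated level.
- Reconcile the 12-month time point (sections 9.1.1 to 9.1.3 and 9.4.2) with the 24-month one in the Synopsis. If 24 months were primary, the 12-month film would also go unused in the primary test.

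The cost is plan wording and a little programming, with no new subjects, visits or films. The downside is a model-based result that assumes missing at random. If dropout depends on the unseen 12-month value, bias is reduced but not removed.

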#### **9.5 Efficacy Patient Population**

All patients enrolled in the study with any follow-up efficacy assessment (radiographic assessment) will be included in the efficacy patient population.

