- Post-surgical muscle and tissue pain;
- Injury to other parts of the spine, such as pedicles and transverse processes that may result in temporary or permanent pain or other neurologic symptoms;
- A solid fusion may put more stress on the disc above or below the fusion, which may lead to other complications over time, such as: loss of proper spinal curvature, abnormal motion, disc degeneration, and pain;
- Cessation of growth of the fused portion of the spine;
- Regional Pain Syndrome (sympathetic nerve response) resulting in burning pain, or other abnormal sensation usually usually in the upper extremities. These include, but are not limited to: autonomic dysfunction, reflexive sympathetic dystrophy, or Homer's Syndrome.

It is anticipated that the adverse events associated with the AccuLIF implant will be similar to those of other spinal implants. Specifically, the AccuLIF implant may:

- loosen, break, or move (migrate) with respect to the other

CONFIDENTIAL

This material is the property of Stryker Spine. Do not disclose or use except as authorized in writing by Stryker.  
Page 34

bones of the spine;

- fail to expand within the interbody space (becomes a static cage);
- move or dislodge from the spine (partially or completely), causing injury to nearby organs and tissues in the lower back including blood vessels, nerve roots, spinal cord, dural sac
- fracture the endplate portion of the vertebra, subside, or dislodge a bone fragment during implantation or over time
- Surgical instruments used in the procedure may break, resulting in loose fragments of instrument material, (which is not implantable grade) in the body. Removal of these fragments may cause damage to bones and/or soft tissues. Non-removal of these fragments may cause adverse allergic reactions or injury to sensitive nearby organs.
- Cause adverse / allergic reactions to implant materials (titanium, stainless steel, cobalt-chromium-molybdenum and silicone rubber).
- The bank bone (for the interbody spacer) may transmit infection
- not be positioned properly in the spine, and not maintain proper spinal curvature
- fracture or perforation of the bones of the spine or dislodge bone fragments that may result in temporary or permanent pain or other neurologic symptoms, or surgery;
- cause adverse reactions (titanium)
- collapse at any point post-operatively;
- require another surgery to correct the problem;
- require another surgery to correct improper placement of the device;

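### Neither sensitivity analysis in section 9.3 tests loss of correction after a subject's last film, and last observation carried forward favours success if correction declines with time

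*Combined protocol and SAP*

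**What the plan says.** - **Missing data (9.3).** "The primary analyses will be based on observed data". The sensitivity analyses are multiple imputation by MCMC and one "using the last observation carried forward". The section gives no imputation model, no list of variables, no missing-data assumption and no analysis with shifted values. It does not name the population for these analyses.
- **Population (9.5).** "All patients enrolled in the study with any follow-up efficacy assessment (radiographic assessment) will be included in the efficacy patient population". One 6-week film is therefore enough to qualify.
- **Films (7.3 to 7.5).** Lateral films are taken at 6 weeks, 3 months and 6 months, so any of these can be the value carried forward.
- **Dropout (9.4.2).** Up to 20% is allowed for, with 100 subjects enrolled.
- **Foreseen risks (12.3).** The implant may "collapse at any point post-operatively", and may subside at implantation or later. No rate or time course is given.
- **Device failure (10.3).** Revising or removing the cage counts as failure and ends the subject's participation. Section 9 has no rule for scoring such a subject in the t-test.
- **Primary time point.** It is 12 months in 9.1.1 to 9.1.3 and 9.4.2, but 24 months under Statistical Methodology in the synopsis.

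**The concern.** Up to a fifth of subjects may have no film at the primary time point, and some will be missing because the cage failed. The sensitivity analyses should show how bad the unseen outcomes would have to be before the conclusion changed. The two that are planned do not. Imputation under its usual assumption gives dropouts the course of similar subjects who stayed. LOCF freezes the last film, which may be only 6 weeks old and, for a revised cage, predates the failure. If correction was lost after the last film, all three analyses could agree and all be too high. That agreement would then be reported as robustness.

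**Working it through.** **Inputs**

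- Test: "a one-sided analysis (alpha=0.05) will be used to assess significance" (9.1.3), "utilizing a one-sided, one-sample t-test" (9.4.2).
- Mean: "it is assumed that the true change in segmental lordosis after 12 months will be 5 degrees" (9.4.2).
- Threshold: "a change of at least 3 degrees is considered clinically meaningful" (9.4.2).
- SD 6, power 90%, 79 evaluable, up to 20% dropout, 100 enrolled (9.4.2).

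**1. The plan's own figure.** For a difference of 5 − 3 = 2 and SD 6, the noncentral t gives 90.2% power at n = 79 and 89.8% at n = 78, so 79 is reproduced. Then 79/0.8 = 98.75, rounded up to 99; the plan enrols 100.

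**2. Mean needed to pass.** At n = 100 and SD 6: 3 + 1.660 × 6/√100 = 3.996.

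**3. Tipping point at the design values.** Take 80 completers at mean 5 and 20 dropouts at mean 5 − L. The overall mean is 5 − 0.2L. The overall SD is √(36 + 0.16L²), where 0.16 = 0.8 × 0.2.

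| L (degrees) | Mean | SD | One-sided p |
|---|---|---|---|
| 0 | 5.0 | 6.00 | 0.0006 |
| 2 | 4.6 | 6.05 | 0.0048 |
| 4 | 4.2 | 6.21 | 0.0281 |
| 5 | 4.0 | 6.32 | 0.0585 |

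The result tips at L = 4.77. With SD held at 6, the tipping dropout mean is (399.6 − 80 × 5)/20 = −0.02, a loss of about 5.0. LOCF reveals none of this: if the dropouts' last films averaged 5, 6 or 7 degrees, its mean is 0.8 × 5 + 0.2 × (5, 6 or 7) = 5.0, 5.2 or 5.4.

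**4. A lower completer mean (4.5, assumed).** The tipping dropout mean is (399.6 − 80 × 4.5)/20 = 1.98, about 2.0. Suppose the dropouts' last films averaged 5. LOCF gives (360 + 100)/100 = 4.6, which passes. If they then lost 4 of those 5 degrees, the full mean is (360 + 20)/100 = 3.8, which fails.

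**5. Cage failures.** Scoring one revised subject with a last film of 5 degrees (assumed), instead of zero change, raises the mean of 100 subjects by 5/100 = 0.05 degrees.

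**6. Simulation.** 600 trials per scenario, n = 100, SD 6, about 20% dropout, correlation 0.7 between adjacent visits. Imputation uses all earlier visits under missing at random, by sequential regression standing in for MCMC. Visit means (6 weeks, 3, 6 and 12 months) either decline (7, 6.5, 6, 5) or stay flat at 5. Apart from SD 6, n = 100 and the 20%, these settings are assumptions. Entries are mean 12-month change in degrees.

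| Scenario | Full data | Observed | LOCF | Imputation |
|---|---|---|---|---|
| (a) Declining means; dropouts lose a further 5 degrees unseen | 3.93 | 4.95 | 5.25 | 4.94 |
| (b) Declining means; random dropout | 4.98 | 4.98 | 5.28 | 4.99 |
| (c) Flat means; dropout follows poor 6-month films | 4.97 | 6.28 | 4.53 | 4.96 |
| (d) Declining means; dropout as in (c) | 4.98 | 6.28 | 4.73 | 4.98 |

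In (a) the full data are significant in 42% of trials; the observed-data, LOCF and imputation analyses are significant in 90%, 98% and 90%. In (b) only LOCF is biased. In (c) and (d) both sensitivity analyses fall well below the observed-data result.

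**The case against.** A reader might infer that the planned sensitivity analyses can only confirm the observed-data result. The documents do not support that. LOCF keeps whatever loss shows on the last film: with 80 completers at 4.5 and last films averaging 1 degree in 20 dropouts, it gives (360 + 20)/100 = 3.8 and fails. Imputation that uses earlier visits also responds to visible loss, as scenarios (c) and (d) show.

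A reader might also infer that LOCF must favour the device. That holds only if correction declines on average. Section 12.3 lists possible complications without rates, and it allows for subsidence at implantation, which a 6-week film could already show. No lordosis trajectory is given.

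Other parts of the plan help. Section 9.1.3 repeats the analysis at every visit and summarises both values and changes, so a decline among subjects still followed would be seen. Migration and subsidence are secondary outcomes (9.1.4). Section 9.1.6 mentions a formal SAP, though only for the literature sources. This is a single-arm post-market study that already plans multiple imputation, and at its design values the result is fairly robust.

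These points narrow the concern but do not remove it. Visit summaries say nothing about subjects after they leave, and no planned analysis lets their unseen values be worse than assumed. The scoring of terminated cage failures remains open.

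**Conclusion.** The concern holds in this form: neither sensitivity analysis tests unobserved loss of correction after the last film. LOCF is biased towards success if correction declines with time, and it would enter a revised or removed cage with its pre-revision film.

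The size depends on the completer mean. At mean 5, SD 6 and 20% dropout, dropouts must lose about 4.8 to 5 degrees on average, nearly the whole assumed gain, to overturn the result. At a completer mean of 4.5, it tips once they average below about 2.0 degrees. It should therefore not be read as showing that the trial is fragile at its design values.

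The tipping figures assume 80 completers and 20 dropouts with the design SD. The direction of LOCF bias, the simulated trajectories and the dropout mechanisms are assumptions. So is the missing-at-random reading of the imputation, which 9.3 leaves unspecified.

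**What to change.** In section 9.3:

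1. Keep the MCMC imputation as the zero-shift case, and state that its model uses baseline and all visit films.
2. Add a delta-adjusted tipping-point analysis in all implanted subjects with a baseline film. Lower the imputed change at the primary time point in steps, and report the shift at which the one-sided lower bound reaches 3 degrees.
3. Within that analysis, do not carry forward pre-revision films for subjects terminated for cage revision or removal. Give them an unfavourable value, for example zero change.
4. Drop LOCF, or label it supportive only.
5. Reconcile the primary time point between the synopsis and section 9. At 24 months, early films would be carried over a longer gap.

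The cost is SAP wording and a few more analysis runs, with no new data. The downside is that the result may look less robust than LOCF would suggest.
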